#### **6.4.2 Developing a prediction algorithm (Research question 2)**

We will follow best-practice guidelines in the development of risk prediction algorithms (Collins, et al., 2015) and will report findings according to the TRIPOD statement (Spitzer RL, 2006) and the guidelines for developing and reporting machine learning predictive models in biomedical research (Luo, et al., 2016). We will adopt an agile approach to algorithm development that will be responsive to data as it accrues and to evolving algorithm performance. As we do not know in advance which combination of predictors and analytical method will be most effective, we will employ the following strategy that enables us to systematically explore the combinations. When we have enough data to begin algorithm development, the data scientists, clinical experts, in consultation with advisory group members, will identify a list of candidate predictors (ready for variable selection using the data) and corresponding methods to develop the initial algorithms; research question 3 will inform discussions of candidate predictors. These will be deployed into the model development sandbox.

We will develop the risk prediction algorithm using Group 1 ( $n = 800$ ), which will then be validated and refined as needed in Group 2 ( $n = 300$ ). Under the assumption that data will be missing at random, multiple imputation will be applied for covariates, any covariates with over 60% missingness will be excluded in the interests of clinical utility (see Section 6.3). The primary outcome will be the binary indication of relapse in either, for example, 7 days (model 1) or 28 days (model 2) from time-of-prediction. For an individual participant, such outcomes will be defined in a 'rolling manner', where we define outcomes at the end of each week (model 1) or each month (model 2). To achieve the best performing model, we will consider a range of analytical models, including (but not limited to): logistic regression, artificial neural networks, support vector machines, random forests, hidden Markov models, and Bayesian approaches. For example, the hidden Markov models will use certain features of an individual's inputs (ASM and PSM) and use the data to calculate for each individual a risk of being in one of a small number of mutually exclusive 'states' which correspond to, for example, remission, deteriorating, relapse. The data will also allow a day-to-day calculation of instability ('entropy') – the likelihood of remaining in that state (Figure 5). Individuals can 'switch' between states. We will include interactions between predictors to allow certain subgroups of individuals to have slightly different 'versions' of the algorithm; that is, tailor the model to subgroups across the heterogeneous target population.

[figure not shown]

Figure 5. Graphical representation of algorithm functionality

Repeated measures for an individual will be appropriately accounted for in any models (e.g. random effects at the participant-level, or use of landmarking techniques). We will use a data-driven approach to select predictors for inclusion in the final risk prediction algorithm. This variable selection procedure will choose from a pre-defined list of candidate predictors (as defined above). For example, candidate predictors will likely be an aggregate of various actively and passively collected observations over a historical time-window as well as demographic variables. For regression-based models (e.g. logistic regression), we will perform variable selection using penalised maximum likelihood (e.g. LASSO L1-regularization), while variable selection is inherent to the machine-learning methods. The use of penalised regression will also help mitigate against overfitting (Riley, et al., 2019).

Internal k-fold cross validation within Group 1 will be used to validate the models, doing this at key landmark times to account for the dynamic (time-updated) nature of an individual's risk estimate. Here, we will quantify predictive performance using calibration (agreement between the observed and expected event proportion, across the full risk range) and discrimination (ability of the algorithm to separate those who have the event from those that do not). For discrimination, we will calculate sensitivity, specificity, positive and negative predictive values at clinically relevant cut-off points, and area under the receiver operating characteristic curve (AUC/C-statistic). For calibration, we will produce estimates of calibration-in-the-large, calibration slope and flexible calibration plots (Van Calster, et al., 2016). The internal validation results will be used to select between the analytical methods (i.e., logistic regression, artificial neural networks, support vector machines, random forests, hidden Markov models, and Bayesian approaches) for each model (i.e. for both models 1 and 2). The primary criteria for algorithm performance will be high specificity (valued by services), with sensitivity a secondary criterion (i.e. we want to maximise specificity whilst ensuring clinically useful sensitivity). This approach to algorithm development on real-time data also offers the potential to be able to stop data collection should an algorithm be developed that meets the requirements for sensitivity and specificity and meets the minimum sample size criteria. The specific requirements for an acceptable level of sensitivity and specificity is a central topic of investigation in this project; we will target performance that is not only statistically significant, but is also acceptable to end-users, clinicians and other stakeholders to maximise clinical utility of the model (i.e. we will establish this iteratively through our PPI and qualitative work).

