#### 3.2 Objectives

There are four objectives:

*Objective 1:* To develop a scalable digital platform that incorporates active symptom monitoring (of psychotic and mood/emotion symptoms), and uses sensor-based behavioural, contextual and environmental data gathered from a smartphone and wearable device.

*Objective 2:* To predict psychosis relapse. We will recruit a cohort of relapse-prone individuals with psychosis and collect information described in Objective 1 to determine whether we can develop a risk prediction algorithm of relapse (we will not test the algorithm in this study; rather, we will collect the data to develop the algorithm, ready for testing in a later clinical trial).

*Objective 3:* To examine the utility of passive data. Passively collected data via smartphones and wearable devices could be used both as predictors of relapse and as a way of reducing the burden imposed by ASM. We will evaluate the data quality and acceptability of different wearable devices (smartwatch vs Fitbit comparison) that integrate with the digital data capture platform in order to assess which is the most feasible and acceptable wearable device to use longer term.

*Objective 4:* To develop an adaptive sampling framework. In the future, we aim to develop an integrated digital platform that not only predicts relapse, but also requests information from an individual at the right time and frequency, thereby minimising the burden on the user, while striking the right balance between ASM vs PSM.

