## **4 Study Design**

### **4.1 Design**

Prospective, observational (non-randomised, non-interventional) study with an in-built process evaluation and assessment of feasibility and acceptability of wearable devices, using commercially available wearable technology and smartphone sensors, representing no change to the usual care or treatments of participants due to participation. There is no control comparison group, or randomised group allocation.

We aim to recruit 1100 relapse-prone individuals with a schizophrenia spectrum diagnosis. To achieve our objectives, we will recruit one cohort (data will be split into two groups):

- i) Group 1 ( $n = 800$ ): in which we will derive and internally test a personalised relapse risk prediction algorithm using ASM items, passively collected behavioural, environmental and contextual data, integrated using machine learning (see statistical analysis section for details of the methods). We will also develop the adaptive sampling algorithm.
- ii) Group 2 ( $n = 300$ ): in which we will apply and temporally test the risk prediction algorithm and the adaptive sampling algorithm from Group 1. Note the adaptive sampling algorithm will not change the data collection in any way, nor will it be used to monitor, prevent or treat psychosis; we will simply use the data collected to test the algorithm.

This design of derivation/internal validation and subsequent temporal validation is appropriate to assess the algorithm's validity. Group 2 acts as a temporal validation set to test the prediction model and the adaptive sampling model on previously unseen individuals (recruited latest in time).

A future study will examine whether our predictive and adaptive sampling algorithms can improve clinical decision-making on early intervention for psychosis relapse (but this will not be tested in the proposed study).

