### **6.4.1 Identification of prognostic variables (Research question 1)**

We will use descriptive statistics and unsupervised machine learning techniques to identify individual variables, and sets of variables, that are most predictive of relapse. Simple or low fidelity/dimension

variables will be analysed in simple regression models to calculate their association with relapse outcomes. High fidelity variables (such as passively collected data from phones) will first be passed through machine learning algorithms such as autoencoders to reduce their dimensionality, then tested for association with relapse. Promising variables will be identified, summarised and passed forward to predictive algorithm development. To be clear, as per best-practice, all identification of prognostic variables will be based on multivariable analyses: we will not use results from univariable analysis to inform predictor selection for the risk model development (which would be a sub-optimal approach).

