
#### **6.4.4 Algorithm validation (Research questions 4, 1 (cont), 6 (cont))**

We will use Group 2 ( $n = 300$ ) to temporally validate both the risk prediction model and the adaptive sampling algorithm developed in Group 1, providing unbiased estimates of predictive performance of each. Here, we will apply the risk prediction model (as developed and selected from Group 1; see above) to each participant in Group 2. We will examine the performance of this final model (in Group 2) in terms of calibration and discrimination using all of the aforementioned metrics. We will additionally aim to determine the clinical utility of the model (within Group 2) using decision-curve analysis, comparing ‘net benefit’ against extremes of a ‘treat-all’ vs. ‘treat-none’ approach across all combinations of risk threshold. The most basic interpretation of a decision curve is that the model with the highest net benefit at a particular threshold has the highest clinical value.

We will compare the performance of the developed algorithm (from Group 1) against existing (previously published) ‘static’ prediction algorithms (that are based only on baseline information and do not make use of the longitudinal or high fidelity data) in Group 2, on all of the metrics above (Research question 4).

For the adaptive sampling algorithm validation, we will subsample the data collected in Group 2 according to the adaptive sampling algorithm and evaluate the reduction in burden on participants and ensure that model performance of the risk prediction model is minimally affected by the reduction in available data. We will then use the validated adaptive sampling algorithm to further tailor the risk prediction model.

Note the adaptive sampling algorithm will not change the data collection in any way, nor will it be used to monitor, prevent, or treat psychosis; we will simply use the data collected to test the algorithm. There will be no change to the usual care or treatments of participants in this study due to testing of the adaptive sampling algorithm.

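### Section 6.4.2 lets the model be refined in Group 2 and 6.4.4 tailors it after validation, so any refined or tailored version would leave the study unvalidated

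*Protocol*

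**What the plan says.** Protocol section 4.1 splits one cohort into Group 1 (n = 800) for derivation and internal testing and Group 2 (n = 300), the people recruited latest. It states that "Group 2 acts as a temporal validation set to test the prediction model" as well as the adaptive sampling model.

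Section 6.4.2 gives Group 2 a second role. The algorithm is developed in Group 1, "which will then be validated and refined as needed in Group 2".

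Section 6.4.4 describes the Group 2 analysis as "providing unbiased estimates of predictive performance of each", meaning of the risk model and of the adaptive sampling algorithm. It says which model is tested: "we will apply the risk prediction model (as developed and selected from Group 1; see above) to each participant in Group 2". After the Group 2 work on adaptive sampling it adds a further step: "We will then use the validated adaptive sampling algorithm to further tailor the risk prediction model".

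Two other places bear on the point. Section 6.4.1, on variable identification, says "Promising variables will be identified, summarised and passed forward to predictive algorithm development" and names no group. Objective 2 in section 3.2 says "we will not test the algorithm in this study", with testing left to a later clinical trial.

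**The concern.** A validation set gives an unbiased estimate only for a model that was fixed without sight of its outcomes. Section 6.4.2 permits changes in Group 2, does not say what would make them necessary, and does not say which version is reported as the result. The obvious trigger would be disappointing performance in Group 2 itself. If the changed version were then scored on the same people, the promise in 6.4.4 would fail for it.

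The tailoring step raises a different problem. It is unconditional and comes after the validation, so the version that leaves the study would not be the version that was tested. Section 4.1 plans a future study of whether the algorithms improve clinical decisions. As written, that study could inherit an untested model described as validated. Deriving and validating this algorithm is the primary outcome in the Study Summary, so the matter is central.

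**Working it through.** **1. The plan's own figure.** Section 6.1 says 800 training participants support 5 to 7 predictors. I used the shrinkage criterion of the sample-size method cited there: p = n_eff × (S − 1) × ln(1 − R²/S).

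- Assumed, not stated: S = 0.9 and 12 monthly windows.
- From 6.1: 15% of maximum R², within-person correlation 0.52, 12-month relapse 25% to 40%.
- n_eff = 800 × 12 / (1 + 11 × 0.52) = 9600 / 6.72 = 1429.
- Event rate per window = 1 − (1 − P)^(1/12): 0.024 at 25%, 0.042 at 40%.
- Result: p = 4.86 and 7.15, which is 5 to 7.

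The stated figure is therefore reproducible, although other window choices give other counts. The present point does not depend on it, except that 5 and 7 predictors are used in step 4.

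**2. Data available.** 800 + 300 = 1100, the whole cohort, so no third set remains. Expected Group 2 participants with relapse: 300 × 0.25 = 75 to 300 × 0.40 = 120.

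**3. Versions of the model and what tests them.**

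| Version | Source | Clean test in this study |
|---|---|---|
| Selected in Group 1 | 4.1, 6.4.2, 6.4.4 | Yes, if scored in Group 2 before any change |
| Refined in Group 2 | 6.4.2 | None |
| Tailored with the adaptive algorithm | 6.4.4 | None; comes after the Group 2 validation |

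**4. Size if a refined version were scored on the same 300.** The answer depends on what refinement means, which the protocol does not say.

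*Intercept or slope recalibration.* With a positive slope this leaves the ranking of participants unchanged, so AUC optimism is 0. Calibration is another matter: an intercept and slope refitted in Group 2 by maximum likelihood give a calibration slope of 1 and no calibration-in-the-large error in Group 2 by construction, so those measures would no longer be tests.

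*Full refit.* This was simulated with 400 runs per setting. Assumptions: one binary outcome per person, a logistic model, 5 or 7 independent predictors of equal strength, and 15% of maximum R². True values come from 40,000 simulated people.

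| Relapse, predictors | Frozen Group 1 model: Group 2 AUC / true | Refit in Group 2: apparent / true | Optimism | Refit slope in new data |
|---|---|---|---|---|
| 25%, 5 | 0.705 / 0.704 | 0.723 / 0.697 | 0.025 | 0.905 |
| 25%, 7 | 0.704 / 0.699 | 0.728 / 0.689 | 0.040 | 0.795 |
| 40%, 5 | 0.692 / 0.692 | 0.706 / 0.688 | 0.018 | 0.919 |
| 40%, 7 | 0.689 / 0.689 | 0.712 / 0.680 | 0.032 | 0.825 |

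Optimism is taken from unrounded means. The frozen model is essentially unbiased. The refit is optimistic by roughly 0.02 to 0.04, and its predictions are too extreme in new data (slope about 0.80 to 0.92). The run-to-run standard deviation of the frozen model's Group 2 AUC was 0.030 to 0.036, so the optimism is about 0.6 to 1.2 of that.

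**The case against.** The strongest reply is that 6.4.4 already names the tested model as the one developed and selected in Group 1 and calls it final. Section 6.4.2 puts cross-validation and the choice of method in Group 1, mentions validation before refinement, and makes refinement conditional. On that reading the Group 1 model gets its clean test. This stands, subject to the order being fixed, which the protocol does not do.

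Four stronger readings are tempting, and the document does not support them.

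- *Nothing in the study is cleanly validated.* The gap concerns only a refined or tailored version.
- *Tailoring inflates the reported results.* It comes after the validation and cannot alter results already obtained. Its product is simply untested. The check in 6.4.4 that performance survives adaptive subsampling concerns the model before tailoring.
- *Variable screening uses Group 2.* Section 6.4.1 is silent on the group, and other sections place derivation and selection in Group 1. The heading of 6.4.4 lists research question 1 as continued without saying what is done. That is an ambiguity, not evidence of leakage. How screening relates to the cross-validation folds is analysis-plan detail.
- *Objective 2 rules out any testing.* The sentence goes on to a later clinical trial, and 4.1 draws the same line for clinical decision-making. The wording is loose rather than a denial of statistical validation.

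On size, the optimism is comparable with the sampling error of the AUC in 300 people, and a light update would give none. That limits how much weight the figures can carry. It does not resolve the conflict between the two sections.

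**Conclusion.** The point holds in a limited form. Section 6.4.2 permits refinement in the set that 4.1 and 6.4.4 present as unseen and as the source of unbiased estimates. The Group 1 model is cleanly tested only if it is scored first, and the protocol leaves that open. Any refined version, and the version tailored under 6.4.4, would leave the study without validation, because no participants remain to test it.

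The conflict and the missing test data follow from the text alone. The size does not: AUC optimism of 0 to roughly 0.02 to 0.04 is illustrative. It assumes that the refined version is the one reported, one outcome per person rather than the rolling weekly or monthly outcomes of 6.4.2, and a full refit as the upper case.

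**What to change.** In 6.4.2, delete the clause that allows refinement in Group 2, so that Group 2 is used for validation only.

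In 6.4.2 or 6.4.4, state that:

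1. the model selected in Group 1 is locked and dated before Group 2 outcomes are analysed;
2. the locked model's Group 2 performance is the primary validation result;
3. any later recalibration, refinement or tailoring with the adaptive sampling algorithm is reported separately as an updated model that has not yet been validated.

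Two minor clarifications should go in at the same time. In 6.4.1, say that variable identification feeding the model uses Group 1 only. In Objective 2, reword the sentence so that what is not tested is the algorithm's use in a later clinical trial, in line with 4.1.

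The cost is wording. The 800 + 300 split, data collection and sample size do not change. Reported performance may be slightly less favourable, and a refined version cannot be called validated. The change needs to be made before Group 2 outcomes are analysed, because refinement guided by them cannot be undone.

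### The option in section 6.4.2 to stop data collection on favourable Group 1 performance does not protect Group 2, and its targets and minimum size are not fixed

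*Protocol*

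**What the plan says.** Protocol section 6.4.2 describes development as follows: "We will adopt an agile approach to algorithm development that will be responsive to data as it accrues and to evolving algorithm performance". On how performance is judged it says "Internal k-fold cross validation within Group 1 will be used to validate the models", and then "The internal validation results will be used to select between the analytical methods". Six method families are named, for each of two models (7-day and 28-day).

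The same section then says that this approach offers "the potential to be able to stop data collection should an algorithm be developed that meets the requirements for sensitivity and specificity". The sentence adds a second condition, that a minimum sample size is also met. On the thresholds it says "The specific requirements for an acceptable level of sensitivity and specificity is a central topic of investigation in this project", and on how they will be set, "we will establish this iteratively through our PPI and qualitative work". No number is attached to the thresholds or to the minimum sample size at this point.

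Section 4.1 describes Group 2 (n = 300) as "previously unseen individuals (recruited latest in time". Section 6.4.4 uses Group 2 for unbiased estimates of performance, decision-curve analysis, the comparison with static models (research question 4) and validation of the adaptive sampling algorithm. Section 6.1 gives the requirement as 1100, made up of 800 for training and 300 for validation. Section 5.6.1 says that everyone is followed for 12 months.

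**The concern.** A decision to stop would rest on Group 1 results, but it would fall first on the people recruited last, who are Group 2. The protocol does not say that Group 2 is exempt, either in recruitment or in follow-up. It also does not say whether the minimum sample size is the number needed to develop the model or the full 1100.

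The decision would also be made on a favourable reading. Performance is viewed as data accrue, several methods compete on the same cross-validation results, and the thresholds are open while this happens. Stopping at the first look where the best method passes selects a random high. The safeguard against that optimism is validation in people not used for development, and this is the part of the study that the stop could shorten. The stated aim is to derive and validate, so half of that aim depends on Group 2 being complete.

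**Working it through.** **Recruitment timetable.** Section 6.2 gives 6.5 participants per month per site at six sites for 29 months. 6.5 × 6 = 39 per month, and 39 × 29 = 1131, which agrees with the target of 1100. Participant 800 enrols at 800/39 = month 20.5 and participant 1100 at 1100/39 = month 28.2.

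**What the minimum could be.** Section 6.1 gives a relapse rate of 25-40%, 15% of maximum variation explained, within-person correlation of about 0.52, and 5-7 predictors. The shrinkage criterion for a binary outcome is n = P / [(S − 1) ln(1 − R²/S)], with S = 0.9 assumed.

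- At 25%: R² = 0.15 × 0.675 = 0.101, giving 83.8 participants per predictor.
- At 40%: R² = 0.15 × 0.740 = 0.111, giving 76.0 per predictor.
- With an assumed design effect of 1.52 (two correlated measures; the protocol does not state the number), 7 predictors at 40% need 809, close to the stated 800. At 25%, 800 supports 6.3 predictors, so the lower end of 5 is not reproduced without further assumptions. The point does not depend on this.
- Five predictors need 381 (40%) or 419 (25%) without a design effect, and up to 637 (25%) with it.

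**Reading A: the minimum is the development criterion.** In enrolment it is met between month 381/39 = 9.8 and month 637/39 = 16.3. Any stop before month 20.5 leaves Group 2 empty. If the minimum must also have completed 12 months, the stop comes later:

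- 419 participants complete at month 10.7 + 12 = 22.7, when about 887 are enrolled, so Group 2 has 87 people.
- 637 complete at month 28.3, when Group 2 is enrolled but has between 28.3 − 28.2 = 0.1 and 28.3 − 20.5 = 7.8 months of follow-up.

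**Reading B: the minimum is all 1100.** Enrolment is safe. If the stop falls when the last Group 1 participant finishes (month 20.5 + 12 = 32.5), Group 2 has 32.5 − 28.2 = 4.3 to 12 months of follow-up. The mean is about 8.15 months, and 8.15/12 = 68% of planned person-time.

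**Precision lost.** A full Group 2 gives 300 × 0.25 = 75 to 300 × 0.40 = 120 relapsing participants. At an assumed sensitivity of 0.60, the 95% half-width 1.96 × √(0.6 × 0.4/n) is 11 to 9 points. With 100 people (25-40 relapsing) it is 19 to 15 points.

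**Optimism at the stop.** This is a simulation on assumed inputs: true sensitivity 55%, target 60% at fixed specificity, 200 relapses (800 × 0.25), six methods with correlated hits (0.6) and six looks. Looks start at 105 events (419 × 0.25) or 159 events (637 × 0.25), so that no look falls below the re-derived minimum at a 25% relapse rate.

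| Rule | Target met |
|---|---|
| One method, one final look | 9% |
| Best of six, one final look | 31% |
| Best of six, six looks from 159 events | about 43% |
| Best of six, six looks from 105 events | about 63% |

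Mean sensitivity at the stop is about 0.62, which is about 7 points above the truth. With correlation 0.9 the last two rows become about 33% and 48%. With true sensitivity 50% (correlation 0.6) they become about 4% and 13%.

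**The case against.** The sentence describes a potential, not a rule, and no automatic trigger is stated. Elsewhere the protocol commits to Group 2 (n = 300) and to 12 months of follow-up for everyone without condition, and research question 4 and the adaptive-sampling validation cannot be answered without Group 2. A reader might infer that the study plans to drop its validation set. The documents do not support that: loss of Group 2 is a possible result of using the option, not a stated intention.

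A reader might also take the minimum sample size to mean only the development criterion. Section 6.4.2 gives no number and section 6.1 says that 1100 are required, so the harsher reading cannot be asserted.

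Nor do the documents say that thresholds will be tuned to observed performance. They come from stakeholder work, and section 3.6 shows that acceptable levels were already being asked about in the Phase 1 interviews. The number of looks and who decides may properly sit in the analysis plan.

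The simulation is simpler than the protocol's criterion, which puts specificity first and requires both measures. Part of the inflation (9% to 31%) is ordinary selection among methods, which occurs without any early stop and which Group 2 exists to correct.

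All of this stands, and it limits the size of the point. It does not remove it. The general commitments do not say that they override the stop option, and both readings of the minimum leave validation exposed. Section 6.4.2 also allows the model to be refined in Group 2, which already weakens that safeguard.

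**Conclusion.** The point holds as a defect in what the protocol permits. As written, data collection could stop on favourable Group 1 results, against thresholds not yet fixed, without protection for the participants recruited last. The consequence ranges from shortened follow-up in a fully enrolled Group 2 (about 68% of person-time in the example) to no Group 2 at all (a stop before about month 20.5). Which applies depends on a minimum that section 6.4.2 does not define. The timetable assumes recruitment at the planned 39 per month.

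The optimism figures (target met in about 43-63% of runs against 31% at one final look, about 7 points too high) are illustrative. True sensitivity, target, number of looks and correlation between methods are assumptions, not protocol figures. Their direction is not in doubt, and an intact Group 2, not used for refitting, would correct them.

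**What to change.** Amend the sentence in section 6.4.2 to say that any early stop may end model development only, and can never shorten Group 2 recruitment (n = 300) or its 12-month follow-up. Require the sensitivity and specificity targets and the numerical minimum sample size to be fixed and dated before algorithm performance is first viewed. State whether that minimum is the development number or the full 1100. Deleting the sentence is an acceptable alternative.

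The cost is one amended sentence and an optional saving given up. No participants are added beyond the planned 1100. The stakeholder work on acceptable levels can continue, but has to report before performance is first viewed.
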